8.5.1.2.2. Goodness of Fit

When assessing terminal elimination phases, the adjusted coefficient of determination for exponential fit (R^2 adjusted) will be used as a measure of the goodness of fit of the data points to the determined line.

Regression-based parameters (AUC_{0-inf} , λ_Z , $t_{1/2}$, and CL/F) will only be calculated if the R^2 adjusted value of the regression line is greater than or equal to 0.7.

8.5.1.2.3. Period of Estimation

The time period used for the estimation of apparent terminal elimination rate constant, where possible, will be over at least 2 half-lives.

Where the terminal elimination rate constant is estimated over a time period of less than 2 half-lives, it will be flagged in the data listings at the discretion of the Pharmacokineticist, and the robustness of the value should be discussed in the CSR.

8.5.1.3. Calculation of AUC

The minimum requirement for the calculation of AUC will be the inclusion of at least 3 consecutive plasma concentrations above the lower limit of quantification, with at least one of these concentrations following C_{max} .

For any partial AUC determination (eg. AUC_{0-24}), nominal time will generally be used for the end of the interval. Actual times for partial AUC intervals may be used at the discretion of the Pharmacokineticist.

AUC_{0-inf} values where the percentage extrapolation is less than 20% will be reported. AUC_{0-inf} values where the percentage extrapolation is between 20 to 30% will be flagged and included in the summary statistics and statistical analysis, whilst AUC_{0-inf} values where the percentage extrapolation is >30% will be reported but excluded from summary statistics and statistical analysis.

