7.3. Pharmacokinetic Population

The PK population will include all subjects who received at least 1 dose of LOXO-305, have at least 1 quantifiable PK concentration, and for whom at least 1 PK parameter can be computed. A subject may be excluded from the PK summary statistics and statistical analysis if the subject has an AE of vomiting that occurs at or before 2 times the median t_{max} .

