8.5. Pharmacokinetic Assessments

8.5.1. Pharmacokinetic Analysis

The following PK parameters will be determined where possible from the plasma concentrations of LOXO-305 using non-compartmental methods performed using Phoenix WinNonlin (Certara USA, Inc.) version 8.1 or higher:

Parameter	Definition
C_{\max}	maximum observed plasma concentration
t_{\max}	time to maximum observed concentration
AUC_{0-24}	area under the concentration-time curve (AUC) from Hour 0 to 24 hours postdose, calculated using the linear trapezoidal rule for increasing and decreasing concentrations
AUC_{0-t}	area under the concentration-time curve (AUC) from Hour 0 to the last measurable concentration, calculated using the linear trapezoidal rule for increasing and decreasing concentrations
$AUC_{0-\infty}$	AUC extrapolated to infinity, calculated using the formula: $AUC_{0-\infty} = AUC_{0-t} + \frac{C_t}{\lambda_z}$ where C_t is the last measurable concentration and λ_z is the apparent terminal elimination rate constant
$\%AUC_{\text{extrap}}$	percentage extrapolation for $AUC_{0-\infty}$
λ_z	apparent terminal elimination rate constant, where λ_z is the magnitude of the slope of the linear regression of the log concentration versus-time profile during the terminal phase
$t_{1/2}$	apparent terminal elimination half-life (whenever possible), where $t_{1/2} = \text{natural log (ln)}(2)/\lambda_z$
CL/F	apparent systemic clearance

Additional PK parameters may be determined where appropriate. The number of points used to estimate λ_z , the lower and upper points used in estimation, λ_z span ratio, and the adjusted coefficient for determination of exponential fit (R^2 adjusted) will be presented in a listing.

The PK analysis will, where possible, be carried out using actual postdose times recorded in the raw data. If actual times are missing, nominal times may be used with sponsor approval.

Concentrations are used as supplied by the analytical laboratory for PK analysis. The units of concentration and resulting PK parameters, with amount or concentration in the unit, will be presented as they are received from the analytical laboratory.

C_{max} and t_{max} will be obtained directly from the plasma concentration-time profiles. For multiple peaks, the highest postdose concentration will be reported as C_{max} . In the case that multiple peaks are of equal magnitude, the earliest t_{max} will be reported.

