8.5.4. Pharmacokinetic Statistical Methodology

All PK concentrations and parameters will be listed.

Summary tables, mean (+ SD) figures, overlaying individual figures, and individual figures by treatment and time postdose will be provided for plasma PK concentrations. All PK concentration figures will be produced on both linear and semi-logarithmic scales, with the exception of figures across all days, which will be produced on the linear scale only. The +SD bars will only be displayed on the linear scale.

Summary tables by treatment will be provided for all PK parameters, with the exception of diagnostic regression-related PK parameters. Summary statistics (n, Mean, SD, CV%, minimum, median, maximum, geometric mean [Geom Mean] and geometric CV% [Geom CV%]) will be calculated for plasma LOXO-305 PK parameters. Excluded subjects will be listed in the PK parameter tables, but will be excluded from the summary statistics and noted as such in the tables.

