8.5.4.1. Statistical Analyses

A statistical analysis will be conducted to investigate the food effect on the single dose administration of LOXO-305 and the drug-drug interaction of Omeprazole on the PK of LOXO-305 for AUC_{0-24} , AUC_{0-t} , AUC_{0-inf} , and C_{max} . The comparisons of interest are:

- 200 mg LOXO-305 (Fed) (test treatment) vs '200 mg LOXO-305 (Fasted) (reference treatment) i.e. Treatment B Vs Treatment A
- 200 mg LOXO-305 + 40 mg Omeprazole (Fasted) (test treatment) vs 200 mg LOXO-305 (Fasted) (reference treatment) i.e. Treatment C Vs Treatment A

The natural log (ln)-transformed³ PK parameters will be analyzed using a mixed model.⁴ The model will include planned treatment sequence, and actual treatment as fixed effects, and subject within planned treatment sequence as a random effect.

For each PK parameter separately, the least squares mean (LSM) for each treatment, difference in LSMs between the fed and fasted treatments, and corresponding 90% confidence interval (CI) will be calculated; these values will then be exponentiated to give the geometric least square means (GLSM), geometric mean ratios (GMR), and corresponding 90% CIs.

[figure not shown]
This procedure is equivalent to Schuirmann's⁵ two one-sided tests at the 0.05 level of significance.

Additionally, the pooled estimate (across all treatments) of the within-subject CV will be calculated, and residual plots will be produced to assess the adequacy of the model(s) fitted.

Example of the SAS code that will be used are as follows:

Mixed Model Analysis

CCI

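### The >30% extrapolation exclusion covers AUC0-inf but not the CL/F derived from it, and the SAP does not say how AUC0-t from such a profile is handled

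*SAP*

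**What the plan says.** SAP 8.5.1.3 grades AUC0-inf by its extrapolated share. Below 20% it is reported. In the middle band, AUC0-inf "values where the percentage extrapolation is between 20 to 30% will be flagged and included in the summary statistics and statistical analysis". Above that, AUC0-inf "values where the percentage extrapolation is >30% will be reported but excluded from summary statistics and statistical analysis". The graded rule names no other parameter.

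SAP 8.5.1.2.2 lists AUC0-inf, λz, t½ and CL/F together as regression-based and says that they "will only be calculated if the R^2 adjusted value of the regression line is greater than or equal to 0.7". Protocol 2.2 also withholds AUC0-inf and CL/F together, along with t½, when a profile shows no terminal log-linear phase.

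For summaries, SAP 8.5.4 says "Summary tables by treatment will be provided for all PK parameters", leaving out only the regression diagnostics, so CL/F is summarised.

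SAP 8.5.1 defines AUC0-t as the area "from Hour 0 to the last measurable concentration, calculated using the linear trapezoidal rule for increasing and decreasing concentrations". The entry test for any AUC is "at least 3 consecutive plasma concentrations above the lower limit of quantification, with at least one of these concentrations following" Cmax. AUC0-t is one of four parameters in the mixed model of SAP 8.5.4.1, which protocol 8.3.2 calls the primary PK analysis. A dosed subject with a quantifiable concentration enters the PK population if he or she is one "for whom at least 1 PK parameter can be computed" (SAP 7.3).

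**The concern.** If CL/F is dose divided by AUC0-inf, an AUC0-inf judged too uncertain to summarise gives an equally uncertain CL/F. The plan would drop the first from the tables and print the second beside the gap. Two other rules, on adjusted R² and on the terminal phase, keep the parameters together; the >30% rule separates them without giving a reason.

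A second, weaker question concerns AUC0-t. When more than 30% is extrapolated, the observed area is less than 70% of that profile's own AUC0-inf. If the profile is short because samples are missing, and the same subject has a full profile under the other treatment, the ratio compares unequal time windows. The SAP does not say whether such a value is flagged or examined.

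**Working it through.** **1. Which rules reach which parameter.**

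| Rule | AUC0-inf | CL/F | AUC0-t |
|---|---|---|---|
| No terminal log-linear phase (protocol 2.2) | withheld | withheld | not affected |
| Adjusted R² below 0.7 (SAP 8.5.1.2.2) | not calculated | not calculated | not affected |
| λz estimated over less than 2 half-lives (SAP 8.5.1.2.3) | no exclusion; discretionary flag on λz | same | not affected |
| Extrapolation >30% (SAP 8.5.1.3) | excluded | not named | not named |
| Vomiting; predose >5% of Cmax (SAP 7.3, 8.5.1.4) | discretionary, by subject, unrelated to extrapolation | same | same |

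The anomalous-value rule in SAP 8.5.1.4 acts on single concentrations. SAP 8.5.4 describes how excluded *subjects* appear in the tables, whereas SAP 8.5.1.3 excludes *values*, so it does not carry the exclusion over to CL/F.

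**2. When the rule can trigger.** Inputs: half-life about 18 h (protocol 1.3.2, stated as uncertain because sampling ran only 0 to 8 h, in patients), median tmax about 2 h (same section), sampling to 168 h (SAP 4).
- Simple exponential: extrapolated share = exp(−ln2 × t_last / t½). At 168 h this is exp(−0.693 × 168/18) = 0.0016, about 0.2%.
- A 30% share at t½ = 18 h needs t_last = 18 × ln(1/0.3)/ln2 = 31.3 h. A one-compartment curve with tmax 2 h (ka about 2.02/h) gives 31.8 h.
- With full sampling, 30% needs t½ = 168 × ln2/ln(1/0.3) = 96.7 h.

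So at anything near the stated half-life, the rule is met only by a profile whose last quantifiable sample comes before about 32 h.

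**3. Whether the other CL/F tests catch it.** A noise-free profile ending at 24 h (assumed sampling grid, last three points for λz) gives adjusted R² of 1.00, 40.3% extrapolated and AUC0-t at 0.60 of the total. It passes the R² test, its AUC0-inf is excluded, and its CL/F remains.

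**4. How far CL/F could be off.** Let e be the true extrapolated share and f the ratio of estimated to true λz. Then CL/F estimated/true = 1 / [(1 − e) + e/f].
- e = 0.4, f = 0.67: 1/(0.6 + 0.597) = 0.835.
- e = 0.4, f = 1.5: 1/(0.6 + 0.267) = 1.154.
- For e from 0.3 to 0.5 and f from 0.67 to 1.5, the range is 0.80 to 1.20.

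With no error in λz the 24 h profile gives a CL/F ratio of 0.997, so the risk comes from error in λz. One value wrong by 20% among 12 similar values moves an arithmetic mean by 0.20/12, about 1.7%.

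**5. Size for AUC0-t.** On the one-compartment curve, a profile ending at 24 h has an AUC0-t of 0.595 of the total. With one such profile on the test side, full data otherwise and a true ratio of 1, the GMR is multiplied by 0.595^(1/N). N is redacted, so it is assumed:
- N = 8: 0.937
- N = 12: 0.958
- N = 16: 0.968
- N = 24: 0.979

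**The case against.** A reader might infer that keeping AUC0-t from a profile with more than 30% extrapolated is itself an error, and that AUC0-t should be deleted along with AUC0-inf. The documents do not support that. AUC0-t is an observed area that does not use λz, so a rule guarding against unreliable extrapolation need not apply to it. Deletion could also bias the comparison. Under SAP 8.5.1.1, values below quantification after the last quantifiable sample are set to missing. A profile that ends early because exposure was low then has a short but genuine AUC0-t, possibly reflecting the food or omeprazole effect under study. Dropping it would pull the ratio towards 1. A badly overestimated half-life could likewise discard a sound area. This objection stands, and it is why AUC0-t should be kept.

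The plan also has partial safeguards. Protocol deviations are weighed before database lock (SAP 7). Subjects with insufficient PK data may be replaced (protocol 4.5). For a λz estimated over less than 2 half-lives, SAP 8.5.1.2.3 allows a listing flag and asks for discussion in the study report; the 24 h example spans at most (24 − 2)/18 = 1.2 half-lives. Where samples reach 24 h, AUC0-24 is still available. These provisions are discretionary or descriptive, and none removes CL/F by rule.

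Finally, subjects are confined from Day -1 to Day 25, so losing every sample after about 32 h is unlikely. Early termination in Period 1 gives no within-subject contrast. In Period 2 of sequence BAC it shortens the reference. In Period 2 of ABC, or in Period 3, it shortens the test. The direction of any shift is therefore not fixed for food, although for omeprazole early termination in Period 3 falls on the test side, because Treatment C is always last.

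**Conclusion.** The CL/F gap is real and is a minor consistency correction. By default, a CL/F derived from a rejected AUC0-inf is summarised. This rests on CL/F being dose divided by AUC0-inf, an assumption that fits its listing as regression-based. CL/F is not in the mixed model, so no primary comparison depends on it.

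For AUC0-t, the gap is only that its handling is not stated. One 24 h test-side profile would multiply the GMR by about 0.96 to 0.97 (N assumed 12 to 16). That figure depends on an uncertain half-life, an assumed curve and an event that should be rare. A reader might go further and infer a substantial risk to the food or omeprazole conclusion, for example by measuring the lower 90% limit against 0.80. The readable documents give neither that limit, nor N, nor a within-subject CV, so no such probability can be drawn from them.

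**What to change.** Extend the last sentence of SAP 8.5.1.3, for instance:

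> *When %AUCextrap exceeds 30%, AUC0-inf and CL/F from that profile are listed but left out of the summary statistics, and AUC0-inf is also left out of the statistical analysis. AUC0-t from that profile is flagged and kept in the primary model. If the profile is short because of early termination or missing late samples, and not because concentrations fell below quantification, the AUC0-t mixed model is repeated without that value as a sensitivity analysis.*

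The subject's other periods stay in. Printing the CL/F formula in SAP 8.5.1 would remove the assumption made here. The cost is the added wording, one fewer CL/F value in a summary if the case arises, and one extra model run.

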8.5.1.4. Anomalous Values

If a value is considered to be anomalous due to being inconsistent with the expected PK profile, it may be appropriate to exclude this point from the PK analysis. However, the exclusion of data must have strong justification and will be documented in the raw data and the CSR.

Embedded BLQ values may be considered anomalous depending on the route of administration and the characteristics of the drug.

Subjects with positive predose values >5% of C_{max} may be excluded from the summary statistics and statistical analysis at the discretion of the Pharmacokineticist.

8.5.2. Presentation of Pharmacokinetic Data

8.5.2.1. Presentation Pharmacokinetic Plasma Drug Concentration Data

The following rules will be applied if there are values that are BLQ or if there are missing values (eg, no result [NR]) in plasma concentration data series to be summarized.

- For the calculation of summary statistics, BLQ values will be set to zero.
- If an embedded BLQ value is considered anomalous within the concentration-time profile, this value will be excluded from the summary statistics.
- Where there is NR, these will be set to missing.
- If there are less than 3 values in the data series, only the minimum, maximum and N will be presented. The other summary statistics will be denoted as not calculated (NC). BLQ is considered a value.

- If all the values are BLQ, then the arithmetic mean, arithmetic standard deviation (SD), median, minimum and maximum will be presented as zero, and the geometric mean and geometric coefficient of variation (CV) will be denoted as NC.
- If the value of the arithmetic mean or median is below the lower limit of quantification, these values will be presented as zero and the geometric mean and geometric CV will be denoted as NC.

8.5.3. Presentation Pharmacokinetic Parameters

For the calculation of summary statistics of PK parameters, all NR and NC values in a data series will be set to missing.

The AUC values will be set to NC if they have been calculated using fewer than 3 concentrations, and/or 3 concentrations if the last is C_{max} .

8.5.4. Pharmacokinetic Statistical Methodology

All PK concentrations and parameters will be listed.

Summary tables, mean (+ SD) figures, overlaying individual figures, and individual figures by treatment and time postdose will be provided for plasma PK concentrations. All PK concentration figures will be produced on both linear and semi-logarithmic scales, with the exception of figures across all days, which will be produced on the linear scale only. The +SD bars will only be displayed on the linear scale.

Summary tables by treatment will be provided for all PK parameters, with the exception of diagnostic regression-related PK parameters. Summary statistics (n, Mean, SD, CV%, minimum, median, maximum, geometric mean [Geom Mean] and geometric CV% [Geom CV%]) will be calculated for plasma LOXO-305 PK parameters. Excluded subjects will be listed in the PK parameter tables, but will be excluded from the summary statistics and noted as such in the tables.

8.5.4.1. Statistical Analyses

A statistical analysis will be conducted to investigate the food effect on the single dose administration of LOXO-305 and the drug-drug interaction of Omeprazole on the PK of LOXO-305 for AUC_{0-24} , AUC_{0-t} , AUC_{0-inf} , and C_{max} . The comparisons of interest are:

- 200 mg LOXO-305 (Fed) (test treatment) vs '200 mg LOXO-305 (Fasted) (reference treatment) i.e. Treatment B Vs Treatment A
- 200 mg LOXO-305 + 40 mg Omeprazole (Fasted) (test treatment) vs 200 mg LOXO-305 (Fasted) (reference treatment) i.e. Treatment C Vs Treatment A

The natural log (ln)-transformed³ PK parameters will be analyzed using a mixed model.⁴ The model will include planned treatment sequence, and actual treatment as fixed effects, and subject within planned treatment sequence as a random effect.

For each PK parameter separately, the least squares mean (LSM) for each treatment, difference in LSMs between the fed and fasted treatments, and corresponding 90% confidence interval (CI) will be calculated; these values will then be exponentiated to give the geometric least square means (GLSM), geometric mean ratios (GMR), and corresponding 90% CIs.

[figure not shown]
This procedure is equivalent to Schuirmann's⁵ two one-sided tests at the 0.05 level of significance.

Additionally, the pooled estimate (across all treatments) of the within-subject CV will be calculated, and residual plots will be produced to assess the adequacy of the model(s) fitted.

Example of the SAS code that will be used are as follows:

Mixed Model Analysis

CCI

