A mixed effect model including planned treatment sequence, period, and actual treatment as fixed effects and subject within planned treatment sequence as a random effect will be used to analyze the natural log (ln)-transformed PK parameters (AUC₀₋₂₄, AUC_{0-t}, AUC_{0-inf}, and C_{max}) and will include calculation of least squared (LS) means and the difference between treatment LS means, as well as their corresponding 90% confidence intervals (CIs). The geometric means ratios (GMR) and their 90% confidence intervals (CIs) of the PK parameter for each treatment comparison will be constructed using the exponentiation of the difference

and the CIs from the mixed effect model. The treatment comparisons of interest include Treatment A versus Treatment B and Treatment A versus Treatment C.

Safety:

All safety assessments, including AEs and SAEs, vital signs measurements, clinical laboratory results, physical examination results, concomitant medications, and 12-lead ECGs, will be tabulated and summarized, where possible, using descriptive methodology, as needed, by timepoint. Unless otherwise specified, baseline value is defined as the last non-missing measurement before administration of LOXO-305 in each treatment period. No formal statistical analyses are planned for the safety data. All safety data will be listed by subject.

Additional details on the analyses will be included in the Statistical Analysis Plan (SAP).

TABLE OF CONTENTS

| TITLE PAGE | | | |
|---|----|--|--|
| SPONSOR APPROVAL | 2 | | |
| INVESTIGATOR AGREEMENT. | 3 | | |
| STUDY IDENTIFICATION | 4 | | |
| SYNOPSIS | 6 | | |
| TABLE OF CONTENTS | 1 | | |
| LIST OF TABLES | 3 | | |
| LIST OF ABBREVIATIONS1 | 4 | | |
| 1. INTRODUCTION1 | 6 | | |
| 1.1. Background1 | 6 | | |
| 1.2. Non-clinical Pharmacokinetics1 | 6 | | |
| 1.3. Summary of Clinical Experience1 | 7 | | |
| 1.3.1. Safety1 | 7 | | |
| 1.3.2. Pharmacokinetics1 | 7 | | |
| 1.4. Study Rationale1 | 8 | | |
| 1.5. Benefit-risk Assessment1 | 9 | | |
| 2. OBJECTIVES AND ENDPOINTS | 9 | | |
| 2.1. Objectives1 | 9 | | |
| 2.2. Endpoints1 | 9 | | |
| 3. INVESTIGATIONAL PLAN | ,0 | | |
| 3.1. Overall Study Design and Plan2 | .0 | | |
| 3.2. Discussion of Study Design | .1 | | |
| 3.3. Selection of Doses in the Study | 2 | | |
| 3.3.1. LOXO-305 | 2 | | |
| 3.3.2. Omeprazole | 2 | | |
| 4. SELECTION OF STUDY POPULATION | 3 | | |
| 4.1. Screening Procedures | 3 | | |
| 4.2. Check-in Procedures (Day -1) | 3 | | |

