1.3.2. Pharmacokinetics

As of 25 October 2019, preliminary steady-state PK data (Day 8 of Cycle 1) were available from 25 patients enrolled in LOXO-BTK-18001. These data demonstrate that LOXO-305 is absorbed after oral administration with a median time to maximum observed concentration (t_{max}) of approximately 2 hours and low clearance (Table 1).

Although the plasma half-life could not be calculated with certainty because of the limited sampling interval (0 to 8 hours), it appears to be approximately 18 hours. Steady-state PK parameters of LOXO-305 in these cancer patients are presented in Table 1. Following administration of the 100 mg QD, 150 mg QD, or 200 mg QD, mean unbound trough plasma levels of LOXO-305 exceeded the concentration required for 90% inhibition (IC₉₀) of the C481S mutant of BTK in vitro.

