Subjects will be randomized to treatment sequences to minimize assignment bias. The 2 treatment sequences will be ABC and BAC. Subjects will be randomly assigned to 1 of the 2 treatment sequences, according to the randomization scheme issued by Covance. A crossover design is used to reduce the residual variability as every subject acts as their own control. The washout period of 7 days between LOXO-305 doses in Treatments A and B and the washout period of 7 days between the doses of LOXO-305 administered in Treatments A or B and the first dose of omeprazole in Treatment C is considered sufficient to prevent carryover effects of the treatments.

Conducting the study in healthy adult subjects mitigates the potential confounding effects of the disease state and concomitant medications.

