5.3. Randomization

Subjects will be assigned a unique identification number upon screening. Subjects who complete the study screening assessments and meet all the eligibility criteria will be assigned a unique randomization identification number (in accordance with the requirements in Section 4.5 and the randomization scheme generated by Covance) prior to the time of the first dose, different from the screening number, and will receive the corresponding product according to the randomization scheme generated by Covance.

Subjects will receive each treatment (A, B, and C) on one occasion. The treatments will be administered on Days 1 (Treatment A or B), 8 (Treatment A or B), and Days 15-18 (Treatment C). The sequences to be used in the randomization will be ABC and BAC.

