8.3.2. Statistical Methodology

The primary PK analysis planned for this study is a mixed effect model including planned treatment sequence, period, and actual treatment as fixed effects and subject within planned treatment sequence as a random effect will be used to analyze the natural log (ln)-transformed PK parameters (AUC₀₋₂₄, AUC_{0-t}, AUC_{0-inf}, and C_{max}) and will include calculation of least squared (LS) means and the difference between treatment LS means, as well as their corresponding 90% confidence intervals (CIs). The geometric mean ratios (GMR) and their 90% CIs of the PK parameter for each treatment comparison will be constructed using the exponentiation of the difference and the CIs from the mixed effect model.

The comparisons of interest are as follows:

- Treatment A compared with Treatment B
- Treatment A compared with Treatment C

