1. INTRODUCTION

This SAP has been developed after review of the clinical study protocol (Final Version 2.0 dated 29 January 2020) and electronic case report form.

This SAP describes the planned analysis of the pharmacokinetic (PK), and safety and tolerability data from this study. A detailed description of the planned TFLs to be presented in the clinical study report (CSR) is provided in the accompanying TFL shells document.

In general, the analyses are based on information from the protocol, unless they have been modified by agreement with Loxo Oncology, Inc. A limited amount of information about this study (eg, objectives, study design) is given to help the reader's interpretation. This SAP must be finalized prior to the lock of the clinical database for this study. When the SAP and TFL shells are approved, they will serve as the template for this study's CSR.

This SAP supersedes any statistical considerations identified in the protocol; where considerations are substantially different, they will be so identified. If additional analyses are required to supplement the planned analyses described in this SAP, they may be performed and will be identified accordingly in the CSR. Any substantial deviations from this SAP will be agreed with Loxo Oncology, Inc. and identified in the CSR.

This SAP is written with consideration of the recommendations outlined in the International Conference on Harmonisation (ICH) E9 guideline *Statistical Principles for Clinical Trials* and ICH E3 guideline *Structure and Content of Clinical Study Reports*.^{1,2}

The document history is presented in [Appendix 1](#).

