10. SIGNIFICANT CHANGES FROM THE PROTOCOL-SPECIFIED ANALYSES

There were no significant changes from the protocol-specified analyses.

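### The SAP drops period from the primary PK model without declaring it, so the food comparison loses its period adjustment and the omeprazole comparison rests on an unstated assumption of no Period 3 effect

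*SAP*

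**What the plan says.** Protocol 8.3.2 defines the primary PK analysis as a "mixed effect model including planned treatment sequence, period, and actual treatment as fixed effects and subject within planned treatment sequence as a random effect". The synopsis describes the same model and adds: "The treatment comparisons of interest include Treatment A versus Treatment B and Treatment A versus Treatment C".

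SAP 8.5.4.1 describes the model for the same log-transformed parameters differently: "The model will include planned treatment sequence, and actual treatment as fixed effects, and subject within planned treatment sequence as a random effect". Period is absent. The section lists B versus A and C versus A as the comparisons of interest, but its sentence on differences of least squares means (LSMs) names only the fed and fasted treatments.

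SAP Section 1 says the SAP supersedes the protocol's statistical considerations and that "where considerations are substantially different, they will be so identified". SAP Section 10 then says: "There were no significant changes from the protocol-specified analyses". The SAP's document history does not mention period either.

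On the design, Protocol 5.3 says: "The sequences to be used in the randomization will be ABC and BAC". Treatments A and B therefore exchange Periods 1 and 2, and C always comes last. Protocol 3.2 gives the reason for the design: "A crossover design is used to reduce the residual variability as every subject acts as their own control".

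**The concern.** This model is the primary analysis for both primary objectives, and the two documents specify different fixed effects without acknowledging it. Two separate problems follow.

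- **B versus A (food).** This is the randomised crossover comparison. Period is estimable here and adjusting for it is routine. Without the term, any shift between Periods 1 and 2 goes into the residual. That widens the interval and raises the pooled within-subject CV that the SAP will report. If the sequences end unequal, the shift also biases the ratio.
- **C versus A (omeprazole).** Treatment C and Period 3 coincide. Any Period 3 effect is indistinguishable from an omeprazole effect. This comes from the design, not from deleting period, but neither document states the assumption. The washout statement in Protocol 3.2 concerns carryover only.

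**Working it through.** **Inputs.** Sequences ABC and BAC (Protocol 5.3); 90% confidence intervals (SAP 8.5.4.1). The number of subjects is blacked out and there is no power calculation, so there is no planned figure to reproduce. Assumed: N = 12, within-subject CV (CVw) 20% (range 15–30%), and a Period 2 to Period 1 shift of 5%, 10% or 25%.

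**Estimability** (design matrix for the two sequences):

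| Model | Rank | B−A | C−A | LSMs of A, B, C |
|---|---|---|---|---|
| Sequence, period, treatment (protocol) | 5 | yes | no | no |
| Sequence, treatment (SAP) | 4 | yes | yes | yes |
| SAP model plus a Period 1 versus 2 contrast coded −1/2, +1/2, 0 | 5 | yes | yes | yes |

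**B−A, balanced sequences.** Let d = ln(1 + shift) and s² = ln(1 + CVw²) = ln(1.04) = 0.0392. Without period, each subject leaves residuals of −d/2 and +d/2, a sum of squares of N·d²/2 on 2(N−1) degrees of freedom. Hence

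SE inflation = √[1 + N·d² / (4(N−1)·s²)].

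- 5% shift: d = 0.0488, √1.017, +0.8%
- 10% shift: d = 0.0953, √1.063, +3.1%
- 25% shift: d = 0.2231, √1.346, +16%

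The reported CVw becomes 20.2%, 20.6% and 23.3%. At CVw 15% and 30%, inflation is 5.4% and 1.4% for a 10% shift, and 27% and 7.6% for a 25% shift.

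**B−A, unequal sequences.** Bias on the log scale = d·(n₁ − n₂)/N.

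- 7:5: 0.0953 × 2/12 = 0.016; 0.2231 × 2/12 = 0.037
- 8:4: 0.0953 × 4/12 = 0.032; 0.2231 × 4/12 = 0.074

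**Coverage of the 90% interval for B−A** (simulation, 20,000 to 40,000 complete-data trials per scenario, N = 12, CVw 20%):

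| Sequences | Shift | SAP model | With contrast |
|---|---|---|---|
| 6:6 | none | 90% | 90% |
| 6:6 | 10% | 91% | 90% |
| 6:6 | 25% | 94% | 90% |
| 7:5 | 10% | 90–91% | 90% |
| 7:5 | 25% | 92% | 90% |
| 8:4 | 10% | 89% | 90% |
| 8:4 | 25% | 84% | 90% |

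At 6:6 with a 25% shift, the mean half-width on the log scale is 0.159 under the SAP model and 0.137 with the contrast.

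**C−A.** With Period 3 shift p₃ (log scale), the SAP model has bias p₃ − d·n₂/N, where n₂ is the number on BAC. The contrast model has bias p₃ − d/2 whatever the imbalance. The two agree when sequences are balanced. A 5% or 10% shift in Period 3 alone cuts C−A coverage to 84% or 69% under both models (6:6).

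**Carryover as a source of shift.** The protocol says of the half-life that "it appears to be approximately 18 hours", and calls it uncertain. Then 168/18 = 9.3 half-lives and 0.5^9.33 = 0.16% remains. LOXO-305 carryover is an unlikely cause, so any shift would come from elsewhere.

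**The case against.** The SAS example is blacked out and may contain period, so the SAP sentence could be a drafting slip. That stands as a limit on knowing which model will be run. The readable text would need correction either way.

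The C versus A confounding is built into the design, and the position of C is open in both documents. True: the protocol model cannot estimate C−A either, so restoring it would not help. What is missing is the explicit caveat.

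The harm to B versus A is hypothetical and mostly small. Subjects are confined on a standard diet, no source of a period effect is identified, balanced sequences give conservative intervals, and the one material loss of coverage needs 8:4 and a 25% shift together. This stands, and it is why the point is not graded higher. Some imbalance is plausible, though: replacement is optional (Protocol 4.5), and the SAP allows exclusion for vomiting, for predose concentrations and for AUC0-inf extrapolation above 30%.

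The contrast does not always improve C−A coverage. If Period 2 alone is 25% higher, coverage is 71% (SAP model) versus 62% (contrast) at 6:6, and 84% versus 63% at 8:4. If the shift persists into Period 3 at 8:4, it is 54% versus 63%. These figures are right. At 6:6 both models have the same bias, and the SAP interval covers more only because its residual is inflated. At 8:4 the SAP bias depends on the imbalance, while the contrast ties C−A to the average of Periods 1 and 2. Neither model removes the confounding.

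A different coding is also defensible: B−A from Periods 1 and 2 with period fitted, and C−A as a separate fixed-sequence comparison.

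**Conclusion.** The concern holds: the SAP text is wrong as written and should be fixed. The readable SAP model omits a fixed effect that the protocol includes in the primary analysis, and Section 10 says nothing changed. With no period effect, the SAP interval for food is correct. With a shift and balanced sequences, the ratio stays unbiased but the interval is too wide: by 3.1% in SE for a 10% shift and 16% for 25%, at the assumed N = 12 and CVw 20%. With a shift and unequal sequences, the food ratio is biased, by 0.016 to 0.074 on the log scale in the cases tried (7:5 and 8:4, shifts of 10% and 25%). The size rests entirely on assumed N, CVw, shift and imbalance; the textual discrepancy and the estimability results do not. For C versus A, a Period 3 effect passes one-for-one into the log ratio under any workable model, so it can only be disclosed.

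**What to change.** In SAP 8.5.4.1:

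1. Keep the pooled three-treatment mixed model and add one fixed contrast coded −1/2 in Period 1, +1/2 in Period 2 and 0 in Period 3. B−A is then period-adjusted, and C−A is taken against the average of Periods 1 and 2. Avoid a plain Period 2 indicator: it ties C−A to Period 1 and raises its variance factor from 0.1667 to 0.2083 at 6:6 (+25%, SE +12%).
2. State: *Treatment C is always given in Period 3, so C versus A cannot be separated from a Period 3 effect.*
3. Reword the LSM-difference sentence to cover both B−A and C−A.

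In SAP Section 10, declare the model change, and reconcile Protocol 8.3.2 and the synopsis with it. Because SAP Section 1 gives the SAP precedence on statistical matters, the Section 10 entry may be enough; a protocol amendment would be an extra cost.

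**Cost.** SAP wording, one coded covariate and one residual degree of freedom (22 to 21 at N = 12). With 6:6 and no shift, the mean B−A half-width is about 0.137 under either model. At 8:4 with no shift, the B−A variance factor rises from 2/12 = 0.1667 to (1/4)(2/8 + 2/4) = 0.1875, so the interval is about 6% wider (0.146 versus 0.137). The C−A factor becomes 1.5/12 + 0.1875/4 = 0.1719, an SE increase of 1.6%. The choice should be fixed before database lock.
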